4.1.1 Inclusion Criteria

Study candidates must meet all the following criteria to be eligible for the study:

- 1. At least 18 years of age.
- 2. Signed informed consent.
- 3. Life expectancy \geq 12 weeks as determined by the Investigator.
- 4. Histologically confirmed adenocarcinoma of prostate per original diagnosis and completed subsequent definitive therapy.
- 5. Suspected recurrence of PC based on rising PSA after definitive therapy on the basis of:

a. Post-radical prostatectomy: Detectable or rising PSA that is ≥ 0.2 ng/mL with a confirmatory PSA ≥ 0.2 ng/mL (per American Urological Association recommendation) or

b. Post-radiation therapy, cryotherapy, or brachytherapy: Increase in PSA level that is elevated by ≥ 2 ng/mL above the nadir (per American Society for Therapeutic Radiology and Oncology-Phoenix consensus definition).

- 6. Negative or equivocal findings for PC on conventional imaging performed as part of SOC workup within 60 days prior to Day 0.
- 7. The Eastern Cooperative Oncology (ECOG) performance status 0-2.
- 8. Adequate recovery from acute toxic effects of any prior therapy.
- 9. Estimated Glomerular Filtration Rate (eGFR) of 30 mL/min or higher.
- 10. Adequate liver function defined as alanine aminotransferase (ALT)/ aspartate aminotransferase (AST) <3 x upper limit of normal (ULN) and total bilirubin <1.5 x ULN (except in the case of Gilbert's syndrome).
- 11. For participants who have partners of childbearing potential: Partner and/or participant must use a method of birth control with adequate barrier protection.

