7.2.7 Total PSA

As part of Screening, baseline PSA will be assessed; additionally, PSA results and dates of 2 previous most recent measurements (prior measurements are needed to assess PSA velocity/doubling time), PSA at initial diagnosis and PSA after initial definitive treatment (nadir) must also be recorded on the eCRF.

Prostate-specific antigen will further be assessed during the Follow-Up as specified in the Schedule of assessments. However, if radiation therapy or other salvage focal therapy (e.g., cryotherapy) is initiated during the study (as long as no concomitant ADT is given), PSA levels must be monitored every 4 weeks from the initiation of the therapy. Prostate-specific antigen response (defined as total PSA decline by \geq 50% from baseline) must be confirmed by a second value within 4 weeks.

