## 7.6 Calculation of PSA Doubling Time and PSA Velocity

The following values of PSA are collecting for this study:

- PSA at Initial Diagnosis
- Nadir PSA after initial definitive treatment
- Most Recent PSA prior to screening #1 and #2
- Screening PSA
- PSA taken during the study at day 90 and 180 (if appliable) or after start of salvage focal therapy (can vary)

PSA doubling time (PSADT) and PSA velocity will be calculated at baseline and during the study and require different definitions. PSA at initial diagnosis will not be used for any calculations of PSA velocity or PSADT.

For calculation of PSADT and PSA velocity at **Baseline**, which will be calculated for all participants:

- PSA Velocity = Slope of the line of best fit using all available data within 12 months prior to screening as well as screening value (excluding at initial diagnosis).
- PSADT = ln(2) / ((ln(PSA value at screening) ln(oldest PSA value within 12 months prior to screening)) / (# of months from oldest PSA value within 12 months prior to PSA at screening))

September 4, 2024 CONFIDENTIAL Page 18 of 46

For calculation of PSADT and PSA velocity for on-study measurements, only the last measure of PSA taken during the study will be used. The following calculations will be done for PSA measurements **Post-Baseline**:

- PSA Velocity = Slope of the line of best fit using all available data on-study, including screening value.
  - o If the participant initiated radiation therapy on-study, the last PSA value is instead the last PSA value PRIOR to initiating radiation therapy.
- PSADT = ln(2) / ((ln(Last on-study PSA value) ln(PSA at screening)) / (# of months from last on-study PSA value to PSA at screening))
  - o If the participant initiated radiation therapy on-study, the last PSA value is instead the last PSA value PRIOR to initiating radiation therapy.
- If a participant has no post-screening value prior to initiation of radiation therapy, they will be excluded from post-baseline calculations of PSADT and PSA velocity.

For the calculation of the line of best fit for PSA Velocity, the following equations will be used for each participant, where  $x_i$  is the date of the measurement in months from screening (screening is x = 0) for each value,  $y_i$  is the PSA value, and n is the total number of datapoints for the participant for that calculation:

$$\overline{X} = \frac{\sum_{i=1}^{n} x_i}{n} \quad \overline{Y} = \frac{\sum_{i=1}^{n} y_i}{n}$$

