#### • Non-evaluable:

 A participant that has either non-evaluable Cu-SAR-bisPSMA PET/CT results for a specific timepoint (Day 0 or Day 1) or has a non-evaluable or inconclusive Reference Standard will not be assigned for that timepoint.

False negative results (region or participant-level) will not be assigned as there is no way to determine whether the disease was initially present, or whether the disease has developed since the acquisition of the baseline and Cu-SAR-bisPSMA imaging. For summarization purposes only, these will be considered "Test Negative" defined as a negative Cu-SAR-bisPSMA PET/CT result within region-level or participant-level and a positive Reference Standard within region-level or participant-level.

Full programmatic details of the algorithm listed above to define Cu-SAR-bisPSMA scan status, reference panel status, and the assessment comparing the two at the subregion-level, region-level, and participant-level will be given in a supplemental analysis document labelled: CLP06\_Primary\_Analysis\_Supplement.xlsx.

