#### 9.14.3.2 Function of Baseline and Other Variables of Interest

CDR, participant- and region-level PPV, and DR of both the Day 0 and Day 1 scans will be summarized by the following variables:

- PSA at baseline:  $<0.5, 0.5 <1.0, 1.0 <2.0, 2.0 <5.0, \ge 5.0 \text{ ng/mL}.$
- PSA doubling time at baseline (PSADT):  $<3.0, 3.0-8.9, 9.0-14.9, \ge 15.0$  months.
- PSA velocity at baseline: 0 to <0.05, 0.05 to <0.10, 0.10 to <0.20, \ge 0.20 ng/mL/y.
- Testosterone at baseline: <230, 230-350, >350 ng/dl.
- Standardized uptake value (SUV) max:  $\leq 2, 2 < 5, 5 < 10, \geq 10$ .
- Initial treatment received (2 categories): radical prostatectomy OR radiation therapy, cryotherapy and brachytherapy.
- Reference Standard Level of Evidence Used: Level 1, Level 2, Level 3
  - Level 1 = histopathology (regardless of imaging results or PSA response being available).
  - Level 2 = imaging results (regardless of PSA response being available) but no contributing histopathology information,

September 4, 2024 CONFIDENTIAL Page 32 of 46

- Level 3 = PSA response only ((i.e., no contribution of histopathology or imaging result information (participant-level only)).
- Size of largest lesion (long axis) identified on  $^{64}$ Cu-SAR-bisPSMA PET/CT central reader scan:  $0 <0.5, 0.5 <1.0, \ge 1.0$  cm.
- Time to Cu-SAR-bisPSMA PET/CT scan from dosing (Day 0 only): 1 − 2 hours, 2 -4 hours.

CDR, participant and region-level PPV, and DR will be summarized for each level of the baseline categorical variables with CDR, PPV, and DR values in each category by central reader. Region-level parameters will only be summarized for the "All regions" category and not the individual regions.

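### PSA velocity is computed per month but binned per year with no stated conversion, and the PSADT groups have no rule for a falling PSA

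*SAP*

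**What the plan says.** SAP 7.6 takes baseline PSA velocity as the slope of the best-fit line through the screening PSA and the values from the preceding 12 months. In the formula, x "is the date of the measurement in months from screening (screening is x = 0) for each value" and no multiplier is applied. Baseline PSADT is ln 2 divided by the monthly change in ln PSA between the oldest value in that window and the screening value. Both are measures "which will be calculated for all participants".

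SAP 9.14.3.2 tabulates CDR, PPV and DR by these measures. One line reads "PSA velocity at baseline: 0 to <0.05, 0.05 to <0.10, 0.10 to <0.20", followed by a top group of 0.20 or more, in ng/mL/y. The line beginning "PSA doubling time at baseline (PSADT" gives groups in months: below 3.0, 3.0 to 8.9, 9.0 to 14.9, and 15.0 or more. The first has no lower limit.

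Protocol 7.2.7 collects "PSA results and dates of 2 previous most recent measurements" and sets no limit on their age or spacing. The stem of inclusion criterion 5 is "Suspected recurrence of PC based on rising PSA after definitive therapy on the basis of"; criterion 5a begins "Post-radical prostatectomy: Detectable or rising PSA that is" at least 0.2 ng/mL.

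No conversion from months to years appears in SAP 7.4, 7.6, 9.14.3.2 or the deviations table in 8.0. The supplement announced in SAP 7.8 offers "Full programmatic details of the algorithm listed above to define" scan status, reference panel status and their comparison. PSA kinetics are not mentioned.

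**The concern.** Formula and groups are each explicit, but on different time scales. Someone who codes the formula exactly and then applies the printed cut-points bins a monthly rate against yearly limits, and an independent programmer following the same text would reproduce that.

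The PSADT gap is separate. A man whose PSA fell has the least aggressive kinetics in the study, yet the arithmetic sends him to the most aggressive group. With about 50 participants split over four groups, even one such entry is visible. What is at stake is how detection and predictive value are described across PSA kinetics.

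**Working it through.** The plan states no result to reproduce, so the check is of units and rules.

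**Velocity, unit.** The slope is Σ(x − x̄)(y − ȳ) / Σ(x − x̄)², with y in ng/mL and x in months, hence ng/mL/month. Multiplying the cut-points by 12 gives what they mean per year if the slope is left unconverted:

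- 0.05 × 12 = 0.6 ng/mL/y
- 0.10 × 12 = 1.2 ng/mL/y
- 0.20 × 12 = 2.4 ng/mL/y

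If ng/mL/y is the intended unit, velocities below 0.05 stay in the bottom group, those at 2.4 or above stay in the top group, and everything between drops at least one group.

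**Velocity, examples (assumed PSA values).**

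- PSA 0.2, 0.3, 0.4 at −6, −3, 0 months: slope = 0.6/18 = 0.033 per month, placed in 0 to <0.05. Per year it is 0.40, the top group.
- PSA 0.5 rising to 2.5 over 12 months: 2.0/12 = 0.167 per month, placed in 0.10 to <0.20. Per year it is 2.0, the top group.

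**Do the cut-points suit a yearly unit?** The documents give no velocity distribution. As an illustration only, I took PSA at 0.2, 0.5, 1, 2 and 5 ng/mL, each with PSADT of 3, 9 and 15 months, assumed exponential growth, and fitted the slope. Of these 15 cases, conversion changes the group of 13 when the PSA values span 12 months, 11 at 6 months and 10 at 1 month. After conversion, 12 (12-month span) or 13 (9 months and shorter) sit in the single top group.

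**PSADT, falling PSA.** Take 0.45 falling to 0.40 ng/mL over 6 months, both above the 0.2 threshold in criterion 5a:

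- PSADT = ln 2 / ((ln 0.40 − ln 0.45)/6) = 0.6931 / (−0.1178/6) = −35.3 months, which is below 3.0.
- Velocity = (0.40 − 0.45)/6 = −0.00833 per month, or −0.10 ng/mL/y. The groups start at 0, so it has none.

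An unchanged PSA makes the PSADT denominator zero, so PSADT is undefined.

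**No earlier value in the window.** If every earlier PSA is more than 12 months old, only the screening value remains. Neither measure can then be computed. This is missing data, not a stable PSA.

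**eGFR (minor).** Protocol 7.2.6 and both schedules report eGFR in mL/min; SAP Appendix 2 grades on mL/min/1.73 m². The mL/min value equal to an indexed limit is limit × BSA/1.73. Body surface area (BSA) is assumed here, because the documents give no body sizes:

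| BSA (m²) | Indexed 60 | Indexed 30 |
|---|---|---|
| 1.6 | 55.5 | 27.7 |
| 1.73 | 60 | 30 |
| 1.9 | 65.9 | 32.9 |
| 2.0 | 69.4 | 34.7 |
| 2.2 | 76.3 | 38.2 |

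If the mL/min value were graded directly, results between 60 or 30 and the tabulated figure would be graded one level too low at BSA above 1.73, and too high below it.

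**Calcium (query).** Other Appendix 2 pairs give about 4 mg/dL per mmol/L: 8.0/2.0 = 4.00, 12.5/3.1 = 4.03, 13.5/3.4 = 3.97. Grade 1 hypercalcemia reads 11.5 mg/dL beside 2.0 mmol/L, a ratio of 5.75. With 2.9, where Grade 2 starts, it would be 3.97.

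**The case against.** The strongest reply is that the groups carry a printed unit, so a careful programmer would convert and nobody would be misplaced. That may happen, but the SAP gives an explicit formula and x-unit, and conversion is a step it does not contain. Nor is it certain which side is the slip. If ng/mL/month was meant, nobody is misplaced and only the label is wrong. The crowding of the illustrative cases in the top group after conversion leaves that possibility open. So a reader might infer that participants will certainly be misclassified; the documents support only that the units are unreconciled and that unconverted binning would misplace them if the yearly label is right.

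A reader might also take 13 of 15 as a share of participants. It is not: the grid is my choice.

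On PSADT, the stem of criterion 5 requires a rising PSA, so a fall should be uncommon. That limits the reach of the gap but does not close it, because 5a accepts a detectable PSA as an alternative to a rising one.

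On eGFR, the indexed CKD-EPI value exists before conversion to mL/min, and no section says which is graded. Misgrading is therefore possible, not established. Shifts within a participant are largely preserved, since eGFR is measured only at Screening and Day 7, when BSA is nearly the same.

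**Conclusion.** Two gaps stand. The velocity slope and its groups are on unreconciled units: unconverted, and with ng/mL/y intended, velocities from 0.05 to just under 2.4 ng/mL/y are grouped too low. The PSADT groups have no rule for a falling or flat PSA, so a negative value is filed with the fastest doublers. How many participants this touches cannot be derived from the documents.

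The effect is confined to the exploratory CDR, PPV and DR summaries by PSA kinetics, in a study with no formal hypothesis testing (SAP 4.1). It would be wrong to infer that the primary CDR or PPV, the sample size or the power are in doubt: none uses velocity or PSADT. The gaps should still be closed, because the tables are prespecified and the repair is small.

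The eGFR item is minor. The calcium item is only a query: the text I worked from was read from PDF and the table is damaged nearby, so the 2.0 may not be in the source.

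**What to change.** 1. **Velocity unit (SAP 7.6 and 9.14.3.2).** State one unit for slope and groups. If ng/mL/y is intended, multiply the slope by 12 or measure x in years, and confirm that the cut-points suit that unit. If ng/mL/month is intended, correct the label.
2. **Stable or falling PSA.** Add this category to both tables with matching treatment of zero: for PSADT, an observed screening PSA equal to or below the oldest value in the window; for velocity, a slope of 0 or less. Start the first velocity group above 0.
3. **Missing.** State that participants with no earlier PSA within 12 months of screening have neither measure and remain missing under SAP 7.3. They do not enter the new category.
4. **Appendix 2.** State that the indexed CKD-EPI value is the one graded. Check the Grade 1 hypercalcemia SI limit against the source PDF and, if it does read 2.0 mmol/L, reconcile it with its mg/dL pair and the start of Grade 2.

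The cost is a few lines in the SAP and programs, one derived eGFR variable from data already collected, and one look at the PDF. No new data are needed.

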## 7.7 Imaging Scans and Reference Standard

The Cu-SAR-bisPSMA PET/CT scans at Day 0 and Day 1 will be interpreted locally in a non-blinded fashion, and centrally by 3 different independent blinded readers in a random order. Each reader will be required to evaluate the PET/CT scans individually for the presence of pathological Cu-SAR-bisPSMA uptake in the prostate bed/gland, pelvic lymph nodes, extra pelvic lymph nodes, visceral/soft tissue and bone. Both local and central interpretations will determine the number of PET-positive lesions in each region and subregion. Table 2 lists the regions and subregions that will be assessed on the Cu-SAR-bisPSMA PET/CT scans.

September 4, 2024 CONFIDENTIAL Page 19 of 46

Table 2 Regions and Subregions Assessed on the Cu-SAR-bisPSMA PET/CT scans

	Anatomic Region	Subregions
1	Prostatic	Prostate Gland or Prostate Bed
2	Pelvic lymph nodes	1. Right Pelvic
		2. Left Pelvic
		3. Other Pelvic
3	Extra pelvic lymph	1. Retroperitoneal
	nodes	

2. Supradiaphragmatic

3. Other Extra-Pelvic

1	Λ':1/Ω 4:	
4	Visceral/soft tissue	1. Lung / Pleura
		2. Liver
		3. Other Soft Tissue / Visceral
5	Bone	1. Pelvic Bone – R
		2. Pelvic Bone – L
		3. Skull
		4. Clavicle – R
		5. Clavicle – L
		6. Scapula – R
		7. Scapula – L
		8. Sternum
		9. Ribcage – R
		10. Ribcage – L
		11. Spine
		12. Extremities
		13. Other bone lesion

The 3 central reader interpretations will be used in the analysis. Subregion, region, and participant-level Cu-SAR-bisPSMA status will be derived. A fourth reader may be used as a backup, and the backup reader results will replace missing reader results that they perform.

For derivations of Cu-SAR-bisPSMA Day 0 or Day 1 positive status:

- A subregion is considered Cu-SAR-bisPSMA PET/CT positive if it has at least one unequivocal PET-positive lesion.
- A region is considered Cu-SAR-bisPSMA PET/CT positive if it has at least one subregion that is considered positive (at least one unequivocal PET-positive lesion).
- A participant is considered Cu-SAR-bisPSMA PET/CT positive if they have at least one region that is considered positive.

September 4, 2024 CONFIDENTIAL Page 20 of 46

The algorithm for determining the status of a subregion for the Cu-SAR-bisPSMA result on Day 0 or Day 1 was changed during the study based on an amendment to the imaging database for collection of non-evaluable results for subregion-level data. This change occurred on 13-Feb-2023 and participants will be flagged in listings as to whether their Cu-SAR-bisPSMA results were collected before or after this change.

Prior to this amendment, subregion status is defined as the following:

- A subregion is considered Cu-SAR-bisPSMA PET/CT positive if it has at least one unequivocal PET-positive lesion.
- If a subregion has only equivocal lesions or no lesions present, the subregion is considered negative.

After this amendment, subregion status is defined as the following:

- A subregion is considered Cu-SAR-bisPSMA PET/CT positive if it has at least one unequivocal PET-positive lesion.
- If a subregion has only equivocal lesions, the subregion is considered negative.
- If a subregion is marked as non-evaluable, then the subregion is non-evaluable and cannot be used in the comparison with the reference standard, this will be excluded from the analysis for that participant.
- If the subregion is **not** marked as non-evaluable but there are no lesions present, the subregion is considered negative.

A reference datapoint is a follow-up histopathology assessment, PSA response, or imaging scan (with the exception of the Cu-SAR-bisPSMA PET/CT scans) occurring between Day 1 and Day 180 that is used to confirm if PC is demonstrated on a participant, region and subregion level. All reference datapoints on study will be evaluated by the expert reference panel to determine the reference standard for each participant. The results will be indicated as "positive", "negative", "inconclusive/equivocal", or "non-evaluable". Additional details are provided in the Reference Standard Review Panel Charter.

Note: An "inconclusive" finding (as described in the protocol and imaging manuals) was assigned to the value of "indeterminate" in the transfer dataset for the central reader histopathology results. As such, for the data analysis and presentation of histopathology findings the terms "inconclusive" and "indeterminate", are considered to have the same meaning and will be used interchangeably. This was implemented in the central reader histopathology database, as for other CDISC SDTM variables that require controlled terminology, "indeterminate" is the defined submission value, with acknowledgement that "inconclusive" is a defined CDISC synonym for this term (to allow for the connection of NCI preferred terms with SDTM submission values).

September 4, 2024 CONFIDENTIAL Page 21 of 46

The composite Reference Standard will be assessed against the Cu-SAR-bisPSMA results at a region-level and a participant-level.

# 7.8 Definitions for Assessments of the Reference Standard against Cu-SAR-bisPSMA PET/CT Results

Assessment of the Reference Standard against Cu-SAR-bisPSMA PET/CT results (i.e., assignment of True Positive, True Negative, False Positive or Non-evaluable status) will be undertaken for Day 0 and Day 1 Cu-SAR-bisPSMA PET/CT results separately.

Assessments of **Region-Level** Reference Standard against the Cu-SAR-bisPSMA PET/CT results:

## • True Positive:

- Histopathology: A region that is Cu-SAR-bisPSMA PET-positive (includes at least one unequivocal PET-positive lesion) and Reference Standard positive is considered a TP region.
- o Imaging: A subregion that is Cu-SAR-bisPSMA PET-positive (i.e., includes at least one unequivocal PET-positive lesion) and Reference Standard positive (i.e., includes at least one unequivocal lesion detected on conventional imaging in that subregion) is considered a TP subregion. The subregion must match between the two assessments. If any region has at least one TP subregion, the region-level status is considered TP.

#### • True Negative:

 A region that is Cu-SAR-bisPSMA PET-negative (no unequivocal PET-positive lesion or only equivocal lesion(s) detected within the subregions) and Reference Standard negative.

#### • False Positive:

 A region that is Cu-SAR-bisPSMA PET-positive (i.e., includes at least one unequivocal PET-positive lesion) and Reference Standard negative based on at least 1 evaluable timepoint.

